## 1.0 Objectives / Specific Aims

The majority of patients suffering from stroke have functional motor impairments that negatively affect their mobility and daily life activities causing a low overall quality of life(1, 2). The most effective way to reduce these motor deficits is with task-specific rehabilitation training(3-7). Recent studies show that noninvasive brain stimulation can enhance task-specific training(8-10). Specifically, repetitive transcranial magnetic stimulation (rTMS) can noninvasively modulate the primary motor cortex(11-13). 1Hz rTMS has a cortically suppressive effect(14), whereas 10 and 20Hz stimulation paradigms induce cortical excitability(11, 12). Increases in excitability last between 10-60 minutes depending on the form of stimulation. These effects are likely long-term depression (LTD) and long-term potentiation (LTP) like neuroplasticity states, as pharmacological NMDA receptor blockade prevents these TMS-induced changes(15).

rTMS is emerging as a potential rehabilitation tool – when delivered to the motor cortex, rTMS can correct post-stroke interhemispheric-imbalance by either reducing excitability in the contralateral motor cortex with 1Hz rTMS(16) or increasing excitability in the ipsilateral motor cortex using 10 and 20Hz rTMS(17, 18). Findings from these studies suggest that rTMS may develop into a promising adjuvant to conventional motor rehabilitation, however a recent large-scale trial was negative however, showing that more work is needed to understand how best to use rTMS for stroke motor recovery.

Can we enhance the effects of rTMS on motor cortex? A different brain stimulation modality, cervically implanted vagus nerve stimulation (cVNS) can enhance neuroplasticity and facilitate rehabilitation, especially when paired with an intervention such as task-specific training(19, 20). There is a new noninvasive form of this method, transcutaneous auricular vagus nerve stimulation (taVNS). This may also facilitate plasticity and is being investigated in the enhancement of motor learning and recovery in a specific paired fashion. The timing of the paired VNS is critical to the desired neuroplastic changes(21-23), as the behavioral effects of paired therapy disappear when behavior is not intricately synchronized with stimulation. Could pairing taVNS with TMS boost the effects of TMS on cortex, and potentially emerge as a stroke recovery tool? As a first step in this direction, we propose a basic, mechanistic pilot study exploring the use of paired taVNS/TMS to further enhance motor cortex excitability in 24 healthy individuals in a 4 visit, randomized, sham controlled, counterbalanced study.

**Aim 1. Determine the effects of taVNS on motor cortex excitability.** We hypothesize that taVNS alone (sham rTMS + active taVNS) will induce increases in motor cortex excitability (post-stimulation compared to baseline). We believe these changes will be of a lesser magnitude than those of TMS alone (active rTMS + sham taVNS) due to the indirect mechanistic approach of taVNS.

**Aim 2. Determine whether taVNS-paired TMS is more effective at inducing cortical excitability than TMS alone.** We hypothesize that pairing two forms of neuromodulation (active rTMS + active taVNS) will increase TMS-induced cortical excitability in the motor cortex when compared to single modality approaches (active rTMS + sham taVNS; sham rTMS + active taVNS). Furthermore, we believe this increase is timing sensitive, and the paired approach will induce larger TMS-induced cortical excitability compared to unpaired neuromodulation (active taVNS + active taVNS).

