### Study Design

We will enroll 40 healthy individuals into a motor excitability prescreening visit (20Hz rTMS to motor cortex flanked by pre- and post-MEP), and from this prescreen cohort subsequently enroll a total of 24 healthy participants (of whom had increases in motor excitability in the prescreen) into a 4 visit, randomized, sham-controlled trial exploring various forms of neuromodulation on cortical excitability (Figure 1). We will first conduct a baseline measure of cortical excitability using a validated motor evoked potential (MEP) paradigm. Participants will then receive 20 minutes of one of four different stimulation conditions (active TMS, sham TMS, active taVNS, sham taVNS, paired taVNS/TMS, unpaired taVNS/TMS). MEPs will be then recorded immediately after stimulation, and every 10 minutes following for 30 minutes.

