### Estimated Difficulties, Limitations and Time Frames

*Estimated Difficulties.* Healthy control MEP studies have been conducted in our laboratory for over 20 years – with minimal difficulty. For this particular study the estimated difficulty will likely be minimizing dropout over 5 experimental visits.

*Limitations.* There are two potential limitations with these studies. The first is tolerability of electrical nerve stimulation of the tragus and earlobe. Although we do not anticipate any issues, drop-out may be an issue due to discomfort of the stimulation.

*Estimated Time Frames.* We plan on completing this study over the next 6-8 months.

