### 11.0 Data Management

Limited demographic and personal health history data will be collected during the phone screen in order to screen out participants with conditions that might confound the research or put them at risk for an

adverse event. All screening data will be kept in a binder in the locked office in the Brain Stimulation Lab as per the requirements of the IRB. Screening data collected from participants who do not qualify for the study will be securely destroyed.

**Power Calculation:** Our proposal utilizes a within-subject design, in which each subject will be their own control. Using the low end of a range of effect sizes (derived from 0.06 partial eta) from prior excitatory TMS/MEP studies (11-13) the proposed study will be sufficiently powered to detect a change in MEP magnitude due to an experimental intervention (paired active/sham rTMS, active/sham taVNS, unpaired taVNS/TMS) using a one-way ANOVA at 80% power and 5% significance level.

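### The four conditions are counterbalanced over four visits, but the only analysis named has no visit term, so any visit-to-visit drift in response would be counted as error and cost power

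*Combined protocol and SAP*

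**What the plan says.** Section 1.0 sets out, for 24 healthy people, a "4 visit, randomized, sham controlled, counterbalanced study". The Study Design part of Section 10.0 confirms 24 participants and four conditions: "Participants will then receive 20 minutes of one of four different stimulation conditions". (The bracket that follows lists six labels; I take four, one per visit.)

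The power paragraph in Section 11.0 says "Our proposal utilizes a within-subject design, in which each subject will be their own control". It takes its effect size as "Using the low end of a range of effect sizes (derived from 0.06 partial eta" and aims to detect "a change in MEP magnitude due to an experimental intervention", "using a one-way ANOVA at 80% power and 5% significance level".

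No section names a visit, period, order or sequence term, gives a model for the MEP data, or says how missed visits are handled. On losses, Section 10.0 says that "the estimated difficulty will likely be minimizing dropout over 5 experimental visits" and adds that discomfort may cause drop-out. Section 3.0 withdraws a participant whose baseline MEPs stay too variable. No rate is given for either.

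**The concern.** Counterbalancing spreads the conditions evenly over visits, so a shift common to everyone at a given visit cancels from the condition means. It does not remove that shift from the residual. A model with condition as its only factor, even with participants accounted for, leaves the between-visit variation in the error mean square. The F-test then rejects too rarely, and the precision that counterbalancing makes available is not used.

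A second, smaller effect appears when visits are missing. Condition and visit number are then no longer exactly balanced, and part of any drift moves into the between-condition contrasts. Aim 2, and the comparison in Aim 1 of taVNS alone with TMS alone, rest on those contrasts.

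**Working it through.** **Inputs from the documents.** N = 24, k = 4 conditions, alpha 0.05, effect 0.06, stated power 80%.

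**Assumptions, none of them stated.** The 0.06 is a partial eta squared; the within-person correlation is rho = 0.5; sphericity holds; all 4! = 24 orders are used once; drift is linear over visits. Drift is expressed in units of the within-person residual SD.

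**Step 1. The plan's own figure.** f² = 0.06/0.94 = 0.0638, so f = 0.253. For a repeated-measures one-way ANOVA, lambda = f²·N·k/(1 − rho) = 0.0638 × 24 × 4/0.5 = 12.26 on 3 and 69 df. Power is 82.6%, and N = 23 is enough for 80%. The stated 80% is thus reproduced, but only under these assumptions. At N = 24 power is 50% with rho = 0, 67% with rho = 0.3 and 97% with rho = 0.7.

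**Step 2. Drift counted as error.** For drift with SD s over the four visits, the visit sum of squares is 24 × 4 × s² = 96s². With every order used once, visit is orthogonal to condition, so without a visit term this all falls into the 69 error df. The expected error mean square rises by the fraction 96s²/69:
- s = 0.25: 96 × 0.0625/69 = 8.7%
- s = 0.5: 96 × 0.25/69 = 34.8%

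With a visit factor the error is on 66 df and is free of drift. Without it, the denominator of F is a noncentral chi-square (3 df, noncentrality 96s²) plus a chi-square on 66 df, divided by 69. Power at lambda = 12.26:

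| Drift SD (residual SD) | Without visit term | With visit term |
|---|---|---|
| 0 | 82.6% | 82.5% |
| 0.1 | 82.0% | 82.5% |
| 0.25 | 79.2% | 82.5% |
| 0.5 | 67.8% | 82.5% |

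Simulation of whole trials gave 79.1% and 67.3% for the last two rows without the term. Under the null, the test without the term rejects 3.6 to 3.8% of the time at s = 0.25 and 1.5 to 1.6% at s = 0.5, against 5% nominal.

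**Step 3. How large these drifts are.** The condition effect itself has SD √(0.0638/0.5) = 0.357 residual SD. Drift of s = 0.5 is 0.5/0.357 = 1.4 times that. The SD of a linear trend over four visits is √1.25 = 1.118 times the step per visit, so s = 0.5 means 0.447 per visit, or 1.34 residual SD from visit 1 to visit 4. That is an extreme case.

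**Step 4. Lost visits.** Within one participant, the difference in visit position between two conditions has variance 10/3. If m of 24 are kept at random and only completers are analysed, the RMS leak of a drift of d per visit into a contrast is d × √[(10/3)/m × (24 − m)/23]. For m = 20 this is 0.170d: 0.034 SD at d = 0.2 and 0.085 SD at d = 0.5, against a contrast SE of √(2/20) = 0.316. If four people stop early and their completed visits are kept, simulation gives 0.030 to 0.074 against an SE of about 0.31. With six stopping early it gives 0.038 to 0.094. The leak is therefore about 10 to 30% of the SE, and over random losses it averages to zero. A visit factor removes it.

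If the orders are simply randomised and not exactly balanced, the same formula without the finite-population factor gives d × √[(10/3)/24] = 0.373d. That is 0.07 to 0.19 SD for d = 0.2 to 0.5, with no losses at all. The documents do not describe the allocation scheme.

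**The case against.** The strongest reply is that the one-way ANOVA stands only in a power paragraph, where nuisance terms are commonly left out. The gap is then a missing analysis plan more than a wrong model. That is fair, but no other analysis is given, so nothing in the plan supplies the visit term.

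Second, the design already limits several sources of drift. Everyone in the crossover has had a prescreen visit with 20 Hz rTMS and MEPs. Stimulator output is reset to a 1 mV MEP before each baseline, and baseline must be stable within 25%. Neuronavigation fixes the target, and thresholds are found by an automated algorithm. This stands for drift in level, site and familiarity. It does not cover drift in the response to 20 minutes of stimulation, which is the outcome, but the documents give no reason to expect that to be large.

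A reader might infer that dropout will bias the results. The documents do not support that. They name dropout as a difficulty without a rate, and nothing links loss to condition. Nor does Section 3.0 say that withdrawal for an unstable baseline happens part-way through the crossover; MEPs are also recorded at the prescreen visit. Finally, the first hypothesis of Aim 1, post-stimulation against baseline within one condition, is not affected by leakage between conditions.

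**Conclusion.** The point holds as a cheap improvement to the analysis. It is not evidence of a biased trial. With complete, balanced data, leaving out visit gives unbiased contrasts, a conservative test and some lost power: about half a point at a drift SD of 0.1, about 3 points at 0.25 and about 15 points at the extreme 0.5. With lost visits, the added error in a contrast is modest chance imbalance, and becomes systematic only if loss depends on condition.

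It would go too far to say that the trial is underpowered because of drift, or that its contrasts will be biased. Drift size, loss rate, correlation and order scheme are all assumptions here, and at small drift the consequence is negligible. What is certain from the text is that the design balances visit order and the only named analysis makes no use of it.

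**What to change.** State the analysis model: participant (random or fixed), condition, and crossover visit number (1 to 4, as a factor), fitted to all completed visits, including those of participants who stop early. Take the between-condition contrasts of Aims 1 and 2 from that model. State also how the visit orders are allocated, so that the degree of balance is known.

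The cost is three of 69 error degrees of freedom, or 82.6% against 82.5% power when there is no drift. No extra participants, visits or procedures are needed. The visit term deals only with drift; if loss turns out to differ by condition, that needs its own discussion.

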The research team is poised to develop a unique, novel, multimodal form of brain stimulation – combining both taVNS and TMS in a time dependent, synchronized manner. We plan to develop this taVNS/TMS system as Aim 1 of this proposal. Critical to understanding the facilitatory effects of pairing taVNS with TMS is the underlying principle of timing the paired stimulus which be better understood. Aim 2 explores the timing effects of paired taVNS/TMS in a classic MEP paradigm, which can help elucidate whether paring of stimulation is critical to the excitability changes. This proposal aims to create a concurrent taVNS/TMS system that can administer both paired- and unpaired- taVNS/TMS stimulation to the motor cortex and facilitate cortical excitability. We will subsequently use this system to investigate whether the timing of taVNS is critical to inducing motor cortex excitability.

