#### **Motor-Evoked Potentials.**

**MEP Recordings.** EMG recordings using Ag/Ag Chloride electrodes will be placed on the subject's hand muscle in order to record motor excitability. The EMG recording electrodes will be connected to a standard CED (Cambridge Electronics Device) amplifier and pre-amplifier. Spike2 software will be used to analyze and record the MEPs. The level of stimulation required to produce a MEP of 1mV will be determined prior to collecting baseline MEPs. Baseline MEPs will be collected at the pre-determined stimulation output for 1mV. Another series of pulses will be analyzed in comparison with the first. If the average amplitude is within 25%, we will proceed with experiment. If not, another series of baseline pulses will be obtained repeating the above process, up to 4 times. If the baseline remains highly variable, the participant will be withdrawn. Following rTMS stimulation, the same pattern of single pulses will be recorded at 0, 10, 20, 30..

The key assumption that underlies the use of MEP measurements as a "read-out" of upstream processes influencing the motor system is that the amplitude of MEPs recorded (via EMG) from peripheral muscles is a product of top-down influences on M1 (such as attention/volitional control), combined with changes in excitatory/inhibitory pre-synaptic (inter)neuronal balance (i.e. due to rTMS at the stimulation site), and the post-synaptic excitability of corticospinal output projections (Bestmann and Krakauer, 2015). This method has been well-established as safe and reliable in the field of TMS research and in the brain stimulation laboratory.

[figure not shown]
**Neuronavigation.** Brainsight Neuronavigation equipment and software will be used (<https://www.rogue-research.com/tms/brainsight-tms/>) to help ensure that the stimulation site remains unchanged during and between recordings and thereby decrease MEP variability.

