## 5.0 Inclusion and Exclusion Criteria/ Study Population

**Inclusion Criteria:** Age 18-80, endorsing good health with no history of mental or physical illness or implanted metal in their body above the level of the neck.

**Exclusion Criteria:** Participants will be excluded for the following: no TMS-induced motor cortex excitability changes in response to 20Hz motor cortex rTMS, any recent psychiatric or physical illness; history of CNS disease, concussion, overnight hospitalization, or other neurologic sequelae, tumors, seizures, frequent or severe headaches; any psychotropic medication taken within 5 half-lives of procedure time; abuse or dependence of drugs (excluding nicotine and caffeine), currently taking medications that lower the seizure threshold; taking any of the stimulants, thyroid medication, or steroids; implanted devices/ferrous metal of any kind; history of seizure or seizure disorder; or inability to determine motor threshold, and TMS resting motor thresholds over 65% of total machine output assessed on experimental visit 1. Pregnant females and children under the age of 18 will be excluded for safety reasons. No vulnerable populations or special classes of subjects will be considered for participation.

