## 10.0 Study Design / Methods

### Screening

[figure not shown]
Up to 40 participants will be screened for inclusion/exclusion criteria, and if enrolled, will attend up to 5 visits at the MUSC brain stimulation laboratory. Participants will sign consent before visit 1, including a urine pregnancy screen (if female). We expect this study to be completed over the span of 6-8 months.

Participants will be screened for taVNS and TMS contraindications before enrolling in the study and written informed consent will be obtained from all participants prior to participation in the experimental paradigm.

For more information on taVNS and TMS screening please see the uploaded taVNS screening form.

[figure not shown]

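### Aim 1 credits taVNS alone with a pre-post rise, and the Aims name no double-sham condition, so the study's sham-controlled label does not extend to that result

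*Combined protocol and SAP*

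**What the plan says.** Section 1.0 describes a study "in 24 healthy individuals in a 4 visit, randomized, sham controlled, counterbalanced study". Its Aim 1 states that "taVNS alone (sham rTMS + active taVNS) will induce increases in motor cortex excitability (post-stimulation compared to baseline"), and adds the belief that this change will be smaller than with TMS alone (active rTMS + sham taVNS). Aim 2 expects paired stimulation (active rTMS + active taVNS) to exceed both single-modality conditions, and to be larger "compared to unpaired neuromodulation (active taVNS + active taVNS"), where the bracket names taVNS twice and rTMS not at all.

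Other sections bear on which conditions exist:

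- Section 10.0, Study Design, announces four conditions but prints six labels, with sham TMS and sham taVNS as separate items.
- Section 10.0, Stimulation Parameters, says the software can deliver active or sham taVNS with active or sham rTMS.
- The power calculation in Section 11.0 gives a third list.
- Section 10.0, Sham Controls, puts the sham coil over electrodes that stimulate the scalp on or near the motor cortex.

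On who is studied, Section 5.0 excludes people with "no TMS-induced motor cortex excitability changes in response to 20Hz motor cortex rTMS", and Section 10.0 enrols "24 healthy participants (of whom had increases in motor excitability in the prescreen) into a 4 visit, randomized, sham-controlled trial".

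Section 2.0 also uses the name Aim 1 for something else: "We plan to develop this taVNS/TMS system as Aim 1 of this proposal". In this point, Aim 1 means the Section 1.0 text.

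**The concern.** A change from baseline within one condition contains everything that happens during the visit: any taVNS effect, drift in MEP amplitude, the effect of repeated single-pulse testing, and the sensory input from the sham rTMS set-up. Removing the last three needs a comparison condition that shares them and lacks active taVNS. For taVNS given without active rTMS, that condition is sham rTMS + sham taVNS, and the Aims name none.

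What is at stake is the conclusion of Aim 1. A non-specific rise could be read as a taVNS effect from a sham-controlled study. A non-specific fall could hide a real effect. The pre-post result cannot tell these apart.

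**Working it through.** **1. Conditions against visits.** The Aims name:

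| Condition | rTMS | taVNS |
|---|---|---|
| taVNS alone | sham | active |
| TMS alone | active | sham |
| Paired | active | active |
| Unpaired | active (Section 10.0) | active |

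Four conditions fill four visits. The fifth visit ("if enrolled, will attend up to 5 visits at the MUSC brain stimulation laboratory") is accounted for by the prescreen: 1 + 4 = 5. Sham taVNS occurs only with active rTMS. The six labels, the software description and the power-calculation list do not define a double sham, and adding one to the four above would make five conditions for four visits.

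**2. Does another feature supply the control?**

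- Comparison with TMS alone: the two conditions differ in both modalities, and the expected result (a smaller change with taVNS) would also appear if taVNS did nothing.
- Counterbalancing addresses visit order, not change within a visit.
- Baseline stability check (Section 3.0, "If the average amplitude is within 25%, we will proceed with experiment"): it acts only before stimulation. Post-stimulation MEPs follow 20 minutes of stimulation and run to 30 minutes after it.
- One-way ANOVA: without a double sham, none of its conditions is a reference without active stimulation.

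**3. The plan's own figure.** Section 11.0 states 80% power at 5% for the ANOVA, from a partial eta of 0.06, without giving the correlation between conditions. Read as partial eta-squared, f² = 0.06/0.94. With four conditions and n = 24, λ = f²·24·4/(1 − ρ) gives power of 0.50, 0.67, 0.83 and 0.97 at ρ = 0, 0.3, 0.5 and 0.7. The statement can be neither confirmed nor called wrong, and this point does not depend on it.

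**4. Illustration of drift.** From the documents: n = 24. Assumed: a two-sided 5% paired t-test (the documents name only the ANOVA), and drift d in SD of the observed change score. The documents give neither the size nor the direction of drift.

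P(significant increase) = 1 − F(t₀.₉₇₅,₂₃; df = 23, ncp = d√24), with t₀.₉₇₅,₂₃ = 2.069 and √24 = 4.899.

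No taVNS effect, upward drift:

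| d | ncp | False significant increase (nominal 2.5%) |
|---|---|---|
| 0.1 | 0.490 | 6.8% |
| 0.2 | 0.980 | 15.4% |
| 0.3 | 1.470 | 29.1% |

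Downward drift makes a false increase rarer (0.8%, 0.2% and 0.04%) but masks a real one. For an assumed true rise of 0.6 SD, ncp = (0.6 − d)√24. Detection falls from 80% without drift to 65%, 47% and 29% at d = 0.1, 0.2 and 0.3.

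In a contrast between two conditions with the same drift, the drift cancels. Simulation of 100,000 trials with independent change scores gave 5.0% to 5.1% rejections in either direction.

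**5. taVNS exposure.** Stimulation Parameters gives taVNS a 50% duty cycle over 20 minutes: 0.5 × 1,200 s = 600 s on. Paired taVNS is concurrent with 2.5 s rTMS trains repeated 40 times: 40 × 2.5 s = 100 s, if taVNS follows the trains. The unpaired text specifies 2.5 s taVNS trains. The documents do not say which schedule the taVNS-alone condition uses.

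**The case against.** The strongest reply is that the protocol misstates nothing. Aim 1 says openly that the test is against baseline. The sham-controlled label describes the study as a whole, which does contain valid sham contrasts, and this is a mechanistic pilot. That stands, and it is why the hypothesis can stay. It does not supply the missing control: Aim 1 is headed as determining the effects of taVNS, and its stated criterion cannot separate those effects from non-specific change.

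A second reply is that the list of conditions is unsettled. Sham TMS and sham taVNS both appear in Study Design, the software can give either form of each modality, and the design figure is not available here. A reader might infer from this point that a double sham is definitely absent. The documents do not go that far: they define none, and the Aims leave no visit for one. The fix must therefore depend on the reconciled list.

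Third, the drift sizes are assumed and would apply to any pre-post test of 24 people. That is correct. The figures show sensitivity to drift and are not evidence that drift occurs in this laboratory.

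**Conclusion.** The point holds for the Aims as written. The inference about taVNS alone rests on an uncontrolled within-condition change, and the sham-controlled label does not reach it. That conclusion is structural and needs no drift figure. The illustrated false-increase rates of 6.8% to 29.1% rest on the assumed test and upward drift of 0.1 to 0.3 SD.

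Three stronger readings are not supported:

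- *That taVNS has no sham control in this study.* Paired and unpaired stimulation can each be set against active rTMS + sham taVNS. Both contrasts concern taVNS added to active rTMS, and neither is the sole sham-controlled estimate.
- *That Aim 1 looks only at baseline.* It also compares with TMS alone, although that comparison cannot establish a taVNS effect.
- *That these Aim 2 contrasts can stand in for taVNS alone.* The taVNS exposure may differ between conditions, as the schedules show.

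Pre-selection on the response to 20 Hz rTMS limits the population under both aims, not Aim 1 alone.

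**What to change.** 1. List the four conditions once, giving the state of each modality. Reconcile the Section 1.0 bracket for the unpaired condition, the six labels and the software wording in Section 10.0, and the list in Section 11.0.
2. If sham rTMS + sham taVNS is among them, state that the Aim 1 test is the between-condition difference in change from baseline against it. Its power then depends on the correlation r of change scores. For an assumed pre-post effect of 0.6 SD and equal SDs, the standardised contrast is 0.6/√(2(1 − r)), so power at n = 24 is 0.51, 0.66, 0.80 and 0.95 at r = 0, 0.3, 0.5 and 0.7.
3. If it is not, add to Aim 1 in Section 1.0: *The taVNS-alone change from baseline is a within-condition result and not a sham-controlled effect of taVNS. Sham-controlled evidence on taVNS comes only from taVNS added to active rTMS: paired, and unpaired, each versus active rTMS + sham taVNS.*
4. Reconcile the taVNS delivery schedules in Stimulation Parameters and say which applies to taVNS alone. If they differ, state that the Aim 2 contrasts concern a different taVNS exposure.
5. State that results under both aims apply to people pre-selected on their response to 20 Hz rTMS, and reconcile Section 5.0 (any change) with Section 10.0 (an increase).

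The cost is editing, and under step 3 a weaker Aim 1 claim. No arm or visit has to be added. A double sham is worth considering only if the sponsor wants a sham-controlled claim for taVNS alone. If it is not already planned, it would need a further visit or displace a condition, and Section 10.0 already names dropout over five visits as the likely difficulty.

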#### **Pairing taVNS with TMS might synergistically increase the effects of TMS alone**

[figure not shown]
Rat models of VNS-paired therapy have demonstrated that timing is critical to the neuroplastic effects of VNS. Rehabilitation training without VNS takes a long time, and VNS alone fails to restore the behavior without the paired training. Delivering VNS immediately following training fails to enhance the training. Therefore, it is important to synchronize stimulation precisely with the paired training.

Aim 1 of this proposal establishes a computerized system that can synchronize two forms of neuromodulation – TMS and taVNS. Using this system, we will investigate whether the timing of taVNS impacts the cortical excitability effects of TMS alone.

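### Aim 2's single-modality comparisons can show that adding taVNS to TMS raises MEPs further, but not that taVNS enhanced the TMS effect, because plain addition gives the same result

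*Combined protocol and SAP*

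**What the plan says.** - **Aim 1 (Section 1.0)** expects that "taVNS alone (sham rTMS + active taVNS) will induce increases in motor cortex excitability", measured against baseline, and adds: "We believe these changes will be of a lesser magnitude than those of TMS alone".
- **Aim 2 (Section 1.0)** asks in its title whether paired stimulation is more effective than TMS alone. Its hypothesis is worded more strongly: pairing "will increase TMS-induced cortical excitability in the motor cortex when compared to single modality approaches". A further hypothesis is that "the paired approach will induce larger TMS-induced cortical excitability compared to unpaired neuromodulation (active taVNS + active taVNS".
- **The framing** is enhancement. Section 1.0 asks "Could pairing taVNS with TMS boost the effects of TMS on cortex", and a subsection title in Section 2.0 reads "Pairing taVNS with TMS might synergistically increase the effects of TMS alone".
- **Conditions (Section 10.0, Study Design):** each participant receives "one of four different stimulation conditions (active TMS, sham TMS, active taVNS, sham taVNS, paired taVNS/TMS, unpaired taVNS/TMS". That is six labels for four conditions. The Aims name no visit with both stimuli sham.
- **Analysis (Section 11.0, Power Calculation):** the only analysis named is a one-way ANOVA, at 80% power and a 5% level, with an effect size derived from a partial eta of 0.06. No contrast is specified, and nothing compares the paired result with the sum of the single effects.

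**The concern.** Saying that taVNS increases the TMS-induced effect is a statement about interaction: TMS does more when taVNS is present. The comparisons offered for it are simple differences between conditions. If taVNS raises MEPs through its own independent route, as Aim 1 allows, those differences are positive even though TMS does exactly what it does alone. The study calls itself mechanistic and a first step towards a stroke recovery tool, so whether the effects add or interact is what a reader will want to know. Every test could be run correctly and the conclusion about mechanism still be unsupported.

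**Working it through.** **1. Algebra.** Let a be the TMS-alone effect, b the taVNS-alone effect and i the interaction, all in change from baseline. Then paired = a + b + i.

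- Paired − TMS-alone = b + i
- Paired − taVNS-alone = a + i

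Aim 1 expects 0 < b < a. With i = 0 both differences are positive. This needs no assumed figures.

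**2. The plan's own figure.** Reading 0.06 as partial eta squared, f = √(0.06/0.94) = 0.253. For a repeated-measures ANOVA with m = 4 conditions and N = 24, λ = f²·N·m/(1 − ρ), with 3 and 69 degrees of freedom.

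- ρ = 0.5: λ = 0.0638 × 24 × 4/0.5 = 12.26, power 82.6%. With f rounded to 0.25, power is 81.7% and 24 is the smallest N that reaches 80%.
- ρ = 0: λ = 6.13, power 50%.

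The sample size is thus reproduced with a between-visit correlation of about 0.5, which the plan does not state. The power is for the overall test, not for any contrast.

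**3. How often addition alone meets both comparisons.** Assumptions: N = 24, change-score SD 1, i = 0, paired t-tests at two-sided 5%, positive results counted, at least 20,000 simulated trials per setting. The four conditions are taken as paired, unpaired, TMS-alone and taVNS-alone.

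Scaling to 0.06 with b = 0.6a: the means are a × (1.6, 1.6, 1, 0.6), whose SD is 0.424a. So a = 0.253/0.424 = 0.595 and b = 0.6 × 0.595 = 0.357. At ρ = 0.5, if 0.06 is taken against the residual variance, both are multiplied by √0.5, giving 0.421 and 0.253. If f is instead taken against the total SD, as in the calculation that reproduces N = 24, they stay at 0.595 and 0.357.

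| a (SD) | b (SD) | ρ | Paired beats both single modalities |
|---|---|---|---|
| 0.595 | 0.357 | 0 | 17% |
| 0.421 | 0.253 | 0.5 | 17% |
| 0.595 | 0.357 | 0.5 | 36% |
| 1.0 | 0.6 | 0 | 50% |
| 1.0 | 0.6 | 0.5 | 80% |
| 1.0 | 0.8 | 0 | 72% |
| 1.0 | 0.8 | 0.5 | 96% |
| 1.0 | 0 | 0 or 0.5 | 2.5% |

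The last row shows that the problem arises only if taVNS has an effect of its own.

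**4. A contrast that does address it.** Paired − TMS-alone − taVNS-alone has expectation i. In every setting above it is significantly positive in about 2.5% of trials.

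- *Precision.* Its variance is proportional to 3 − 2ρ, against 2 − 2ρ for a pairwise difference. The standard-error ratio is √(3/2) = 1.22 at ρ = 0 and √(2/1) = 1.41 at ρ = 0.5.
- *Drift.* If MEPs drift by s within a session whatever the stimulation, the contrast estimates i − s. With a = 0.8, b = 0.5 and ρ = 0.5, a drift of +0.2 or −0.2 SD moves its two-sided error to about 10%. A downward drift mimics synergy.
- *Delivery.* Section 10.0 (Stimulation Parameters) gives taVNS a 50% duty cycle for 20 minutes, but rTMS 2.5 s on and 10 s off, which is 2.5/12.5 = 20%. If taVNS-alone and paired taVNS follow different patterns, b is not the same quantity in both conditions.
- *Scale.* Relative increases of 1.5 and 1.2 that multiply give 1.8; adding the same increments gives 1.7. Effects additive in log MEP are therefore more than additive in mV, and the plan fixes no scale.

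**The case against.** The strongest reply is that the plan never commits to a synergy claim. Aim 2's title asks only whether paired stimulation beats TMS alone, and paired > TMS-alone answers that whether or not the effects add. Synergy appears once, as a possibility, in a background subsection title. No rule says that beating the single modalities means synergy. This stands: a reader might infer that the plan treats the comparison as proof of synergy, and the documents do not say so. What remains is the hypothesis wording about TMS-induced excitability, the opening question about a boost, and the absence of any analysis that could support either.

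A second reply is that the plan contains a safeguard. Section 2.0 makes timing a central question of Aim 2, and with equal stimulation plain addition predicts no difference between paired and unpaired. This stands in part. A reader might infer that paired > unpaired would establish synergy, but it tests timing. An interaction that does not depend on timing would give no difference, and an inhibitory interaction confined to the unpaired condition would give a difference without synergy. The comparator is also unclear: Aim 2 writes it as taVNS plus taVNS, while Section 10.0 describes taVNS given during rTMS and concurrently with it, much as in the paired condition.

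A third reply concerns size. A reader might infer that a positive Aim 1 makes a positive Aim 2 likely under addition. The documents do not support that in general. Scaled to the plan's 0.06, the rate is 17% to 36%, and among trials with a positive Aim 1 it is about 12% to 33%. Rates of 50% and above need larger effects than the plan assumes: TMS 1.0 SD with taVNS 0.6 SD corresponds to a partial eta squared of about 0.15 at ρ = 0.

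**Conclusion.** The point holds as a limit on interpretation. Under Aim 1's own hypothesis, the single-modality comparisons in Aim 2 cannot separate enhancement of the TMS effect from addition of a separate taVNS effect, and no named analysis can. They remain a valid answer to Aim 2's title question.

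The logic rests on Section 1.0 alone. The rates rest on assumed effect sizes, SD, between-visit correlation and a four-condition reading of the design: about 17% (36% under the scaling that reproduces N = 24) at the plan's 0.06, about 50% to 80% with TMS 1.0 SD and taVNS 0.6 SD, and more with larger taVNS effects, against 2.5% for an additivity contrast in the synergy direction. The wording should be corrected and the contrast added before the data are analysed.

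**What to change.** 1. **Limit the Aim 2 claim.** State that paired > TMS-alone will be read only as showing that adding taVNS to TMS raises MEPs more than TMS alone.
2. **Keep paired versus unpaired as a timing test.** Do not read it as proof of synergy. First reconcile the definition of the unpaired condition in Aim 2 with that in Section 10.0.
3. **Add one secondary contrast for any boost or synergy statement:** paired minus TMS-alone minus taVNS-alone, in change from baseline, with a 95% confidence interval, on a scale fixed in advance (for example log MEP).
4. **State what the contrast assumes:** no within-session drift, since the Aims name no double-sham visit, and the same taVNS delivery in the taVNS-alone and paired conditions. The 50% duty cycle and the 2.5 s on, 10 s off pattern must be reconciled, as must the six condition labels with the four conditions.

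Cost: revised wording and one contrast from data already collected, with no extra visit or participant. The contrast's standard error is about 22% (ρ = 0) to 41% (ρ = 0.5) wider than a pairwise one, the stated power does not cover it, and a synergy claim becomes harder to reach.
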